3.8 Data Management and Statistical Analysis

Data collection: Structured electronic case report forms were designed and implemented for data acquisition, covering baseline characteristics, imaging features and proposed diagnoses of the two examinations, biopsy information and pathological results, follow-up records, and adverse event profiles.

Data entry and verification: Independent entry by two individuals, employing logical consistency checks and scope verification, with disputed data corrected based on original records.

When baseline measurement data conform to normal distribution, mean \pm standard deviation is used for description, and independent samples t-test is

employed for intergroup comparisons. If normal distribution is not met, median (interquartile range) is used for description, and Mann-Whitney U test is applied for intergroup comparisons. For baseline categorical data, case count (percentage) is used for description, and chi-square test or Fisher's exact test is utilized for intergroup comparisons.

Primary outcome measures: The accuracy rates of both examinations were calculated separately as (true positives + true negatives) / total cases. The difference in accuracy rates between the two examinations was compared using a paired chi-square test to determine statistical significance, with the calculated difference and its 95% confidence interval (CI) reported. Sensitivity and specificity were assessed using the McNemar test. For secondary outcome measures, count data comparisons between groups were performed using chi-square tests, with rate differences and their 95% CIs reported. When data followed a normal distribution, independent samples t-tests were used for intergroup comparisons. For non-normally distributed metric data, Mann-Whitney U tests were employed for intergroup comparisons.

The incidence rate of adverse events was calculated as the total incidence rate and the incidence rates of various events, with chi-square test or Fisher's exact test used to compare intergroup differences.

Subgroup analysis was performed to evaluate the stability of the results, with all findings presented as two-sided. A p-value <0.05 was considered statistically significant.

4、Alternative diagnostic and therapeutic methods available

Study participants may opt out of this research without any adverse impact on their access to conventional treatments. For this condition, standard therapeutic approaches include: performing only traditional colposcopy, with biopsy taken when necessary based on endoscopic findings to guide subsequent management plans. If

biopsy is not required, regular follow-up examinations are recommended. Traditional colposcopy has a long history and is performed by highly skilled practitioners, but its imaging quality is suboptimal, resulting in poor visualization of the cervical canal.

This may lead to unnecessary biopsies and endocervical curettage (ECC).

5、 Data Management and Information Confidentiality

During the study period, personal information such as the names and genders of study participants will be replaced with codes or numbers and strictly confidential. Only the relevant physicians will be aware of their data, ensuring robust protection of participants' privacy rights. Study findings may be published in academic journals, but no personal information of study participants will be disclosed.

If study participants consent to participate in this study, all their medical records will be reviewed by relevant personnel from the research institution initiating this study and relevant authoritative agencies, or by an independent ethics committee, to assess the appropriateness of study procedures.

6、 Adverse Event Management

Study participants required the insertion of specula and application of acetic acid or iodine tincture to the cervical and vaginal mucosa. Biopsy may be necessary when indicated. Mild pain, mucosal trauma, or slight vaginal bleeding are considered normal phenomena. If major vaginal bleeding, allergic reactions, or infections occur during or within 24 hours post-procedure (before follow-up completion) and cannot be ruled out as unrelated to the procedure, they shall be classified as adverse events. The procedure must be immediately discontinued, and the research team will provide prompt medical intervention to participants while reporting the incident within 24 hours.

VII. Ethical Principles and Requirements for Life Sciences and Medical Research

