3.3 Study duration: March 2026 – March 2030

3.4 Sample Size and Calculation Basis

Based on research reports, the diagnostic accuracy of colposcopy for low-grade lesions is only approximately 43.4%, while the diagnostic accuracy for high-grade lesions ranges from 59% to 76%. A domestic multicenter study demonstrated that traditional colposcopy has a specificity of 75.1% and a sensitivity of 70.2% in detecting high-grade cervical lesions. Control group indicators (P0): According to data, traditional colposcopy achieves a diagnostic accuracy of approximately 59-76% for high-grade lesions (HSIL+). The lower limit of 59% is adopted as the calculation benchmark. Experimental group expected indicators (P1): It is hypothesized that high-definition magnified electronic colposcopy can significantly improve detection rates. A 20-percentage-point improvement is required to achieve statistically significant clinical significance, with diagnostic accuracy potentially reaching around 79%. Prevalence in target population: Literature reports indicate that among participants undergoing colposcopy, the proportion of cases ultimately pathologically confirmed as high-grade lesions (HSIL+) ranges from 20% to 40%, with a set threshold of 30%. Statistical power (Power, $1-\beta$): Set at 90%, with $\alpha = 0.05$ (two-tailed).

Methods: Sample size estimation was performed using the sample size calculation formula for paired design diagnostic tests (McNemar test). A minimum of 212 study participants with complete paired data and valid gold standard results were required, accounting for a dropout rate of 10%-20%. The final planned total sample size was 270 cases.

Continuous enrollment was employed to include all eligible participants who met the inclusion criteria and consented to participate in the study until the target sample size was achieved. To balance potential biases arising from examination

sequence, a simple randomization method was used to assign participants to two distinct examination sequences (Sequence A group: initial observation and image acquisition using a conventional optical colposcope (magnification 7.5-15x), followed by endoscopy (preset magnification 90-120x); Sequence B group: initial examination using an endoscope, followed by colposcopy).

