3.6 Methods and Procedures

The same study participant was randomly assigned to groups A and B according to sequence randomization, with examination sequences conducted in two groups.

Procedure for Evaluation Method 1 (Colposcopy): Study participants were placed in the lithotomy position. After routine disinfection and draping, a speculum was inserted. Traditional colposcopy was performed at designated time points (after saline administration, 1 minute and 2 minutes post-acetic acid test, and post-iodine test). The colposcopy specialist interpreted imaging features, recorded proposed diagnostic opinions, and marked suspected lesion sites (denoted as Point Y). The cervical surface was conceptualized as a clock face centered on the cervical os, with

the 12 o'clock position representing the top of the cervix. For example, Y6 indicates suspected cervical lesion at the 6 o'clock position under colposcopy.

[figure not shown]
Evaluation of Probe Method 2 (High-Definition Electronic Magnification Endoscopy + Image Enhancement Technology): Procedure Flow: In the same study participants, high-definition electronic magnification endoscopy combined with image enhancement technology was used to observe the cervix and vagina and acquire images at specified time points (after saline administration, 1 minute after acetic acid test, 2 minutes after acetic acid test, and after iodine test). The endoscopist interpreted the images based on characteristic features, recorded proposed diagnostic opinions, and marked suspicious lesion sites on the schematic diagram (denoted as N-point, e.g., N3 indicates suspected cervical lesion at point 3 under endoscopic evaluation; lesions simultaneously identified as suspicious by colposcopy and endoscopy are labeled as T-point, e.g., T9 indicates suspected cervical lesion at point 9 according to both examinations).

Biopsy specimens from suspicious sites (2-4 mm per tissue block, totaling 2-4 tissue blocks) were submitted for examination. Endoscopists and colposcopists were unaware of each other's interpretation results. Pathologists conducted microscopic examination of the biopsy specimens and issued pathological diagnosis results (pathologists were unaware of the grouping and proposed microscopic diagnosis results).

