For study participants who showed no suspicious lesions on conventional colposcopy or endoscopy, informed consent was obtained to voluntarily opt for biopsy. Those who chose biopsy had their pathological results compared with the proposed microscopic diagnosis using the gold standard. Participants opting against biopsy underwent 6-12 month follow-up HPV and TCT testing. Those with negative follow-up HPV/TCT results, abnormal HPV/TCT findings, or persistent negative results after colposcopy evaluation or colposcopic biopsy pathology were classified

as true negatives (suboptimal microscopic diagnosis negative with follow-up gold standard confirmation). Participants with \geq CINII or VAINII findings after 6-12 month colposcopic biopsy were categorized as false negatives (no suspicious lesions detected microscopically but confirmed high-grade lesions by follow-up gold standard). Image feature analysis was performed between experimental and control groups, with accuracy validated through pathological or follow-up results. Adverse events were recorded 24 hours post-examination (when vaginal swabs were removed after biopsy) for participants undergoing both instrument-based examinations.

technology roadmap :

3.7 Evaluation indicators:

Primary outcome measure: accuracy rates of the two examinations, with histopathological results or follow-up outcomes serving as the gold standard.

Secondary outcome indicators: sensitivity, specificity, positive predictive value, negative predictive value, AUC, and lesion recognition rate (referring to the ability to identify suspicious lesions through high-definition magnified endoscopy in cases that are difficult to detect with conventional colposcopy).

Efficacy indicators: clarity of lesion margins and visualization capability of microvascular structures (including resolution of point-like, clustered, and spiral patterns), assessed using a 4-point Likert scale: 1=poor, 2=average, 3=good, 4=excellent.

Safety indicators: Examination-related adverse event incidence rate (e.g., bleeding, infection, mucosal injury or perforation during the procedure), postoperative complication rate within 24 hours (e.g., lower abdominal discomfort, vaginal bleeding, fever), and examination tolerance (assessing the proportion of study participants who discontinued the examination midway or requested termination of the procedure).

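### True positive is undefined and no rule ties each test's marked sites to the biopsy result, so a test can be credited with a lesion that only the other test located

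*Protocol*

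**What the plan says.** Section 3.6 (Methods and Procedures) has the colposcopist record an opinion and map what was seen: "marked suspected lesion sites (denoted as Point Y". The endoscopist does the same: "marked suspicious lesion sites on the schematic diagram (denoted as N-point". For example, "N3 indicates suspected cervical lesion at point 3 under endoscopic evaluation". Sites marked by both tests are coded T. Tissue is then taken: "Biopsy specimens from suspicious sites (2-4 mm per tissue block, totaling 2-4 tissue blocks) were submitted for examination". The protocol does not say how these blocks relate to the Y, N and T sites.

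Section 3.7 (Evaluation indicators) names the primary outcome as "accuracy rates of the two examinations, with histopathological results or follow-up outcomes serving as the gold standard". Section 3.8 computes it for each test as "calculated separately as (true positives + true negatives) / total cases" and compares the two by a paired chi-square test. The cases are women. Section 3.4 says "A minimum of 212 study participants with complete paired data and valid gold standard results were required" and then "The final planned total sample size was 270 cases".

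Section 3.6 describes true negatives and false negatives only for women in whom no suspicious lesion was seen. True positive is not defined anywhere.

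**The concern.** Take a woman with a colposcopy mark at Y6 that proves benign and an endoscopy mark at N3 that proves high-grade. Endoscopy found the lesion and colposcopy did not. At the level of the woman, though, colposcopy was positive and the reference is positive, so colposcopy can be counted as right. She does not fit the described false negative, because colposcopy did see something suspicious. The mirror case credits endoscopy.

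The stated objective is accuracy in detecting lesions, and the primary comparison is paired. Only discordant pairs inform that comparison, and in this woman a real disagreement is recorded as agreement. The test that misses more lesions has more to gain. If endoscopy locates more, as the protocol hypothesises, most of the borrowed credit goes to colposcopy. Its sensitivity is then overstated and the difference understated.

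**Working it through.** **The plan's own figures.** The protocol gives no rate of site disagreement, so there is no stated figure to reproduce on this point. The minimum of 212 cannot be checked either, because the McNemar formula needs the proportion of discordant pairs and none is given. The point does not depend on 212.

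**Inputs from Section 3.4.** Colposcopy sensitivity 70.2%, colposcopy specificity 75.1%, HSIL+ prevalence 30%, planned accuracy 59% against 79% (20 points).

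**Assumptions, not in the protocol.**
- The 70.2% is the share of diseased women in whom colposcopy marks the true site.
- Endoscopy locates 65% of the lesions colposcopy misses, and 85% overall.
- In diseased women, a test that misses the lesion has a false mark elsewhere with probability f = 1 − 0.751 = 0.249, for both tests.
- Any mark counts as a positive call.

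**Step 1: one-test-only finds, as a share of diseased women.**
- Endoscopy only: (1 − 0.702) × 0.65 = 0.1937
- Both: 0.85 − 0.1937 = 0.6563
- Colposcopy only: 0.702 − 0.6563 = 0.0457

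**Step 2: borrowed credit under location-blind scoring.**
- Colposcopy: 0.1937 × 0.249 = 0.048, or 4.8 points of sensitivity
- Endoscopy: 0.0457 × 0.249 = 0.011, or 1.1 points
- Range for colposcopy: 0.298 × 0.50 × 0.15 = 0.022 to 0.298 × 0.80 × 0.40 = 0.095, or about 2 to 10 points

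**Step 3: net effect on the differences.**
- Sensitivity: 0.048 − 0.011 = 0.037. With equal f this is f × (0.85 − 0.702) = 0.249 × 0.148.
- Accuracy: 0.30 × 0.037 = 0.011, or 1.1 points
- For f from 0.15 to 0.40: 0.148 × f = 0.022 to 0.059 in sensitivity, and 0.7 to 1.8 points in accuracy

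**Step 4: discordant pairs lost.** In diseased women, 24.9% of one-test-only finds become concordant. With 212 × 0.30 = 63.6 diseased women, 63.6 × 0.2394 = 15.2 such pairs fall to 15.2 × 0.751 = 11.4.

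Pairs favouring endoscopy also come from women without disease in whom endoscopy clears a colposcopy false positive, and there site plays no part. As shares of all women:
- Endoscopy-only finds: 0.30 × 0.1937 = 0.0581, of which 0.0581 × 0.249 = 0.0145 are lost
- Colposcopy false positives: 0.70 × 0.249 = 0.1743
- Endoscopy clears 75% of these: 0.1307, so the loss is 0.0145 / (0.0581 + 0.1307) = 7.7%
- Endoscopy clears 25%: 0.0436, so the loss is 0.0145 / (0.0581 + 0.0436) = 14%

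**Second route, reading 70.2% as a per-woman figure.** Assume endoscopy sensitivity 0.79 and independent tests. Then 0.702 × 0.79 = 0.555 of diseased women are positive on both. If colposcopy marked only the wrong site in 5% to 30% of them, its located sensitivity would be 0.674 to 0.536, and its accuracy would fall by 0.8 to 5.0 points. This is the gross change for colposcopy, before any matching correction to endoscopy. The first route corresponds to a mismatch of 0.048 / (0.6563 + 0.048 + 0.011) = about 7%, near the lower end.

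**The case against.** The strongest reply is that the protocol nowhere says such credit is given. A reader might infer a location-blind definition of true positive, or a single pathology result per woman, but the text states neither. The Y, N and T codes are what scoring by site would need, and the case report form in Section 3.8 covers biopsy information and pathology. Detailed scoring rules are also often left to a statistical analysis plan. All of this stands, and it limits the point to what can happen under the rules as written. It does not remove the point. The protocol itself fixes the accuracy formula and a false-negative description that leaves out a wrongly placed mark, and whether a block can be traced to its site is settled at biopsy. The figures in Section 3.6 were not available to me. If one of them ties block to site, that rule belongs in the text.

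The Y6/N3 example also assumes that a mark at Y6 is a positive call for the target lesion. Each examiner also records a proposed diagnosis, and the threshold is not stated. That is correct, and it is an assumption here.

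Two stronger readings fail. One is that a quarter of all pairs favouring endoscopy are lost. The quarter applies only to finds in diseased women, and over all such pairs the loss is roughly 8% to 14%. The other is that the flaw could produce a false claim of superiority. If endoscopy locates more lesions and false-mark rates are similar, the bias runs against that claim.

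**Conclusion.** The concern holds as a gap in the definition of the primary outcome. It arises only when both tests are positive at different sites and only one is right; a test that marks nothing gains nothing. On the assumptions shown, colposcopy sensitivity is inflated by about 5 points (range 2 to 10), the sensitivity difference falls by about 4 points, and the accuracy difference by about 1 point against a planned 20. None of these sizes can be taken from the protocol alone, because it gives no rate of site disagreement, false marks in diseased women, or overlap between the tests. The effect on the primary outcome is too small to support a reading that the conclusion would be overturned. The effect on sensitivity is larger. The severity is should-fix, because the remedy is cheap and blocks that cannot be traced to a site cannot be attributed later.

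**What to change.** Keep the woman as the unit and state the following in Sections 3.6 to 3.8:

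- **True positive, for each test:** target histology at one of its own marked sites (Y or T for colposcopy, N or T for endoscopy).
- **False negative, for each test:** target histology found only at sites that it did not mark.
- **Location tolerance:** fix in advance when two marks are the same site, for example adjacent clock positions, so that one lesion marked at Y5 and N6 is not split.
- **Vaginal lesions:** add a site code, since the clock face covers only the cervix.
- **Marked but unsampled sites:** treat as unverified, not as a miss, and vary this in a sensitivity analysis.
- **Blinding:** number blocks neutrally and link them to the site code only on the case report form, so that labels do not show pathologists which test marked the site.
- **Sensitivity analysis:** report the location-blind result per woman alongside the primary result.

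The protocol should also state how the 2-4 blocks relate to the two tests' marked sites. No biopsy rule is proposed here.

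The cost is protocol wording and one link on the case report form, with no extra participants. The stated sensitivities of both tests will be slightly lower.

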3.1 Study Design

Study type: Paired diagnostic test design (diagnostic accuracy study with intra-participant comparisons)

Randomization method: sequential randomization

Blind method: Open (blinding of personnel interpreting pathological diagnostic results)

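### Section 3.8 assigns independent-group tests to PPV, NPV and the image-quality scores, although both examinations are done in the same women

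*Protocol*

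**What the plan says.** Section 3.1 of the protocol names the design: "Paired diagnostic test design (diagnostic accuracy study with intra-participant comparisons". Section 3.6 confirms that endoscopy is not given to a separate arm: "In the same study participants, high-definition electronic magnification endoscopy combined with image enhancement technology was used to observe the cervix and vagina". Section 3.4 shows what is randomised: "a simple randomization method was used to assign participants to two distinct examination sequences". Sequences A and B therefore differ only in which examination comes first.

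Section 3.7 lists the outcomes: "Secondary outcome indicators: sensitivity, specificity, positive predictive value, negative predictive value, AUC, and lesion recognition rate". It also lists lesion-margin clarity and microvessel visualization, "assessed using a 4-point Likert scale: 1=poor, 2=average, 3=good, 4=excellent". Section II makes both the predictive values and the imaging characteristics secondary objectives, each to be compared between the two methods.

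Section 3.8 gives accuracy a paired chi-square test, and sensitivity and specificity the McNemar test. For what remains it says "For secondary outcome measures, count data comparisons between groups were performed using chi-square tests, with rate differences and their 95% CIs reported", and for measured data "independent samples t-tests were used for intergroup comparisons. For non-normally distributed metric data, Mann-Whitney U tests were employed for intergroup comparisons".

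**The concern.** In a within-woman comparison, the variance of the difference between the examinations includes the covariance of a woman's two results. Chi-square, independent-samples t and Mann-Whitney U tests set that covariance to zero. Two views of the same cervix would be expected to agree to some degree. Leaving the covariance out then gives a standard error that is too large, intervals that are too wide and a test that rejects too seldom.

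At stake are two declared secondary objectives: predictive values and image quality. For these the plan would discard the efficiency that a paired design provides. PPV and NPV raise a further difficulty. Their denominators are the women called positive (or negative) by each examination, so they differ between examinations yet share many of the same women. Neither the ordinary chi-square nor McNemar fits that structure.

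**Working it through.** **Which outcomes are affected.**

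- Accuracy (primary): paired chi-square. Not affected.
- Sensitivity and specificity (secondary): McNemar. Not affected.
- PPV and NPV: fall under the chi-square sentence. Affected.
- Image-quality scores: fall under the independent t or Mann-Whitney sentences. Affected.
- Lesion recognition rate: affected only if it is calculated for both examinations and compared, which its definition does not make clear.
- AUC: no test named.

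**What the groups could be.** Section 3.6 says "Image feature analysis was performed between experimental and control groups", which points to the two examinations; the tests then ignore the pairing. The baseline comparisons in section 3.8 can only be sequence A against B. If that meaning carries over, the tests are valid for the sequences but do not compare the examinations. The wording fails the stated objective on both readings.

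**Size for scores and common-denominator rates.** The protocol has no figure for this point to reproduce and states no within-woman correlation, so the correlation ρ is assumed and varied. With equal variances σ² and n women:

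- unpaired variance of the difference = 2σ²/n
- paired variance = 2σ²(1 − ρ)/n
- SE ratio r = 1/√(1 − ρ)
- true two-sided alpha of the nominal 5% test = 2[1 − Φ(1.96 r)]
- power of the unpaired test where the paired test has 80% = Φ((1.96 + 0.842)/r − 1.96)

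| Assumed ρ | SE ratio | True alpha | Power (paired test = 80%) |
|---|---|---|---|
| 0 | 1.00 | 5% | 80% |
| 0.3 | 1/√0.7 = 1.20 | 1.9% | 65% |
| 0.5 | 1/√0.5 = 1.41 | 0.6% | 51% |
| 0.7 | 1/√0.3 = 1.83 | 0.03% | 34% |

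**Check at the planned size.** The 212 complete pairs in section 3.4 are taken as given; the point does not depend on how that number was derived. Assume both rates are 0.70. The unpaired 95% half-width is 1.96 × √(2 × 0.70 × 0.30/212) = 8.7 points. At ρ = 0.5 the paired half-width is 1.96 × √(2 × 0.70 × 0.30 × 0.5/212) = 6.2 points.

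Simulation of binary outcomes (200,000 runs per setting, 212 pairs) agrees:

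| Correlation | Type I error, unpaired (both 0.70) | Power for 65% v 75%, unpaired | Power for 65% v 75%, McNemar |
|---|---|---|---|
| 0 | 5.1% | 62% | 61% |
| 0.3 | 2.0% | 64% | 77% |
| 0.5 | 0.6% | 66% | 89% |
| 0.6 | 0.2% | 68% | 95% |

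McNemar held close to 5% type I error throughout.

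For 4-point scores (3,000 runs per setting, 212 pairs, assumed latent shift 0.25 SD), at latent correlation 0.3 / 0.5 / 0.7:

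- Mann-Whitney: type I error 2.3% / 1.0% / 0.1%; power 69% / 72% / 75%.
- Wilcoxon signed-rank: type I error about 5%; power 78% / 89% / 97%.

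**PPV and NPV.** The formula above needs a common denominator. For predictive values the overlap is only partial and depends on how often the examinations agree, so these factors show direction, not size.

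**The case against.** The strongest reply is that the main conclusions are safe. The primary comparison and the sensitivity and specificity comparisons are already paired, and under positive correlation the error on the rest is conservative. No power target is stated for the secondary outcomes. All of that stands.

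The correlation is also unknown. Section 3.6 has two specialists reading separately, each unaware of the other's result, so a low correlation for subjective scores cannot be excluded. At zero correlation nothing is lost. This stands too, and is why the table starts at 0.

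The scores are listed in section 3.7 under efficacy indicators rather than secondary outcomes, so their link to the section 3.8 sentences is inferred. Section II makes imaging characteristics a secondary objective, and no other test is offered, so the inference is reasonable.

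A reader might infer more than the document supports:

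- That all secondary outcomes, or every reported interval, are wrong. Sensitivity and specificity are secondary outcomes with a paired test, and the primary difference is reported after a paired test with no interval method fixed.
- That lesion recognition rate is mishandled. Section 3.7 describes it as what endoscopy finds in cases that are hard for colposcopy, which is not clearly a rate for both examinations.
- That the missing AUC test and primary interval formula are errors. They are unstated, and a statistical analysis plan may supply them.
- That the p-values are invalid whatever the groups mean. If the groups are A and B, the tests are valid but answer a different question.

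**Conclusion.** The point holds for the secondary comparisons other than sensitivity and specificity, chiefly PPV, NPV and the image-quality scores. The tests named for them either ignore the pairing or do not compare the examinations, depending on what the groups are. The contrast with the explicitly paired tests in the same paragraph makes it hard to read the independent-sample tests as paired.

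The size rests on an assumed correlation. Over 0 to 0.7, the inflation of the standard error for scores and common-denominator rates runs from none to 83%. The consequence is imprecision and missed differences. The trial's main hypothesis test is not threatened, and an excess of false positives would require negative within-woman correlation, which is not the natural expectation here.

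**What to change.** In section 3.8, state that comparisons between the two examinations are paired, and replace the independent-group tests for those comparisons:

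- Image-quality scores: Wilcoxon signed-rank test, or an ordinal GEE clustered on participant.
- Any rate with the same denominator for both examinations: McNemar test, with a paired confidence interval for the difference.
- PPV and NPV: a generalized score test, or relative predictive values with a paired confidence interval.
- AUC, if it is compared: a method for correlated ROC curves.

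Keep independent-group tests for comparisons between sequences A and B, such as baseline data and adverse events recorded after both examinations, and say explicitly that the groups there are the sequences.

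This changes wording only. It needs no new data and no change in sample size. Making it before the data are analysed avoids choosing the method after the results are seen.

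### Adverse events are compared between unnamed groups with an unpaired test although each woman has both examinations, and sections 3.7 and 6 disagree on mucosal injury and slight bleeding

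*Protocol*

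**What the plan says.** Section 3.1 describes a "Paired diagnostic test design (diagnostic accuracy study with intra-participant comparisons". Section 3.6 has colposcopy first described, and then: "In the same study participants, high-definition electronic magnification endoscopy combined with image enhancement technology was used to observe the cervix and vagina". The only randomised groups are orders of examination: under section 3.4, "a simple randomization method was used to assign participants to two distinct examination sequences", A being colposcopy then endoscopy and B the reverse.

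Tissue is taken as one set from whatever sites look suspicious: "Biopsy specimens from suspicious sites (2-4 mm per tissue block, totaling 2-4 tissue blocks) were submitted for examination". Women in whom nothing suspicious is seen may decline biopsy and be followed up instead (section 3.6).

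On recording, section 3.6 states: "Adverse events were recorded 24 hours post-examination (when vaginal swabs were removed after biopsy) for participants undergoing both instrument-based examinations". No other time of recording is described, and no rule links an event to colposcopy, endoscopy or biopsy.

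On analysis, section 3.8 gives total and event-specific incidence rates, then chi-square or Fisher's "exact test used to compare intergroup differences". The groups are not named. The same section uses a paired test for accuracy.

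On definition, section 3.7 lists "Examination-related adverse event incidence rate (e.g., bleeding, infection, mucosal injury or perforation during the procedure", a separate 24-hour complication rate that includes lower abdominal discomfort and vaginal bleeding, and a tolerance measure (examinations stopped midway). Section 6 states: "Mild pain, mucosal trauma, or slight vaginal bleeding are considered normal phenomena". It goes on to classify major bleeding, allergic reactions and infections as adverse events.

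**The concern.** Chi-square and Fisher's test compare independent groups of people. This design has no two groups that differ in which device they received: every participant is meant to receive both. The planned comparison therefore has to be read either as device against device, where the same women are counted twice, or as order against order, where the devices are balanced. In neither reading does the named test fit a question about the safety of endoscopy relative to colposcopy. A p-value above 0.05 could still be taken as reassurance about the device.

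The second issue is what gets counted. If two sections treat the same finding differently, the incidence rate depends on which section the recorder follows.

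**Working it through.** The protocol gives no event rates and no figure for this comparison, so there is nothing of its own to reproduce. All event rates and correlations below are assumptions for illustration. The planned total of 270 comes from section 3.4, and the two-sided 0.05 level from section 3.8.

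**Reading 1: groups are sequences A and B.** Let *c*, *e* and *b* be the chances of an event from colposcopy, endoscopy and biopsy. If both examinations are completed and order has no effect, the chance of at least one event in the 24-hour record is 1 − (1 − *c*)(1 − *e*)(1 − *b*). This is the same in A and B whatever *e* is, so the null hypothesis of the test is true for every device difference. With *c* = 1%, *b* = 10%, 135 women per sequence and 20,000 simulated trials per row:

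| Endoscopy rate *e* | Chance of an event, both sequences | Chi-square rejects | Fisher rejects |
|---|---|---|---|
| 1% | 11.8% | 4.6% | 3.0% |
| 5% | 15.4% | 5.1% | 3.5% |
| 10% | 19.8% | 5.0% | 3.4% |
| 20% | 28.7% | 4.8% | 3.5% |

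For example, the last row is 1 − 0.99 × 0.80 × 0.90 = 0.2872. A 20-fold change in the endoscopy rate leaves rejection at or below about 5%.

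**Reading 2: groups are the two examinations, 24-hour events.** A woman has one 24-hour record covering both examinations and any biopsy. If it is entered under both devices, the two rates are identical and the difference is 0. If it is to be entered under one device, a rule is needed, and the protocol states none.

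**Reading 2, events that can be tied to one examination.** The data are then paired. Take 10% for each device and a within-woman correlation of 0.5.
- Variance assumed by the unpaired test, times *n*: 0.10 × 0.90 + 0.10 × 0.90 = 0.18.
- Actual variance, times *n*: 0.18 − 2 × 0.5 × 0.09 = 0.09.
- The standard error is overstated by √(0.18/0.09) = 1.41, so the effective cut-off is 1.96 × 1.41 = 2.77 and the true two-sided error about 0.6%. Simulation (270 women, 4,000 runs) gives 0.6% for the unpaired test and 5.8% for McNemar.
- With 10% against 15% and the same correlation, power is about 38% unpaired and 71% by McNemar. At zero correlation both are about 42%.

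These McNemar figures use the large-sample form; the exact form is more conservative.

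**What the 24-hour data can support.** This is an absolute rate for the combined session. For 0 events in 270, the exact two-sided 95% upper limit is 1 − 0.025^(1/270) = 1.36%.

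**Definitions side by side.**

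| Finding | Section 3.7 | Section 6 |
|---|---|---|
| Mucosal injury or trauma | Counted as an adverse event | Normal |
| Bleeding | Counted, no severity threshold | Slight: normal. Major: adverse event |
| Pain or discomfort | Under the separate 24-hour complication rate | Mild pain: normal |

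The first row is a direct clash. The second could be settled by severity, but section 3.7 gives no cut-off. The third is not a contradiction, because section 6 classifies adverse events and section 3.7 lists discomfort under a different rate.

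**The case against.** The best defence is that safety is neither an objective nor part of the hypothesis, that no claim of equal safety is planned, and that attribution rules and form fields are often left to an analysis plan or case report form, neither of which is shown. Those facts stand, and they keep the point away from the primary outcome. They do not rescue the test. The protocol itself names an unpaired method for a within-participant design, and no later analysis can recover which examination caused an event if that was not noted at the time.

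Several stronger inferences are tempting, and the documents do not support them.

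- *The comparison can never show a device difference.* This is too strong. An event during one examination, or a midway stop, belongs to an identifiable examination. The sentence on 24-hour recording does not say that nothing is noted sooner. For such events the unpaired test is inefficient rather than powerless.
- *Every woman's record includes a biopsy.* It does not, since women with no suspicious site may decline.
- *The two safety sections contradict each other throughout.* Only mucosal injury against mucosal trauma clashes directly. Section 6 also does not say that its list of adverse events is exhaustive.
- *The reported rate would swing by a known large amount.* The protocol gives no event rates from which to size this.

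**Conclusion.** The point stands in limited form. The named test does not suit the design under either reading of the groups. Between sequences it can detect only an order effect, with rejection at no more than about 5% for any device difference, assuming no order effect and both examinations completed. Between devices it ignores the pairing, and for 24-hour events it has no basis for attribution. The loss from ignoring pairing depends on the assumed correlation: 38% against 71% power in the example, and none at zero correlation. The safety comparison would be uninterpretable as written; the accuracy analysis is untouched.

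The definitional issue is narrower: one direct clash (mucosal injury or trauma) and one missing threshold (bleeding).

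**What to change.** - In section 3.8, drop the between-group test for 24-hour events. Report them for the combined session, overall and by type, with exact 95% confidence intervals, split by biopsy yes or no.
- Record events and early termination that occur during an examination against that examination. Compare only these between devices, with the exact McNemar test.
- Reconcile section 3.7 with section 6 on mucosal injury and on the severity at which bleeding counts. Which events count is for the sponsor to decide. Section 6 ties its classification to stopping the procedure and to 24-hour reporting, so wording must not be carried from one section to the other without considering that link.

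The cost is revised wording, one extra field on the case report form, and a narrower safety comparison. The field has to be in place when the examinations are done, because attribution cannot be added afterwards.
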